Section 4.3 Exclusion Criteria – Angiographic Exclusion Criteria	Current version : Patient has a previously placed arterial stent distal to or including the origin of the ipsilateral great vessel (includes a stent anywhere in the ICA, CCA, or brachiocephalic artery).	Subjects who have a stent in the ipsilateral side to target lesion will be excluded. This includes internal and common carotid arteries as well as the innominate artery if applicable.
	Previous version : Patient has previously placed stent in the ipsilateral carotid artery.	
Section 4.3 Exclusion Criteria – Angiographic Exclusion Criteria	Current version : Patient has known mobile plaque, thrombus, or excessive calcification in the aortic arch.	Subjects who have excessive calcification in the arch will be excluded
	Previous version : Patient has known mobile plaque or thrombus in the aortic arch.	
Section 4.3 Exclusion Criteria – Angiographic Exclusion Criteria	Addition of Exclusion Criteria #9: Patient has aneurysmal carotid bifurcation on the ipsilateral side.	Additional criteria included to exclude subjects with aneurysmal carotid bifurcation on the treatment side.
Section 4.3 Exclusion Criteria – Angiographic Exclusion Criteria	Addition of Exclusion Criteria #10: Patient has tortuous anatomy or disease morphology which would prohibit the safe placement of guide catheter, sheaths, embolic protection systems or stent systems within the access or target vessel	Additional criteria included to exclude subjects with tortuous anatomy that will prevent safe introduction of interventional equipment.

Section 5.1 Study Procedures and Evaluation Schema Section 5.2 Schedule of Events	Addition of : "Obtain review by Screening Committee" Multiple changes to reflect new screening process.	Update to reflect current process for Screening Committee review. Update to reflect current process for Screening Committee review.
Section 5.3 Informed Consent Process	Current version : All patients must provide written informed consent prior to submission of pre-procedure imaging and medical history to the Screening Committee for review (refer to Section 5.5 for details) and prior to and study related procedures being performed.	Update to reflect current process for Screening Committee review.
	Previous version : All patients must provide written informed consent prior to any study related procedure being performed.	
Section 5.5 Pre- Screening/Screening	Current version : Inclusion and exclusion criteria assessed: confirmation is required by Screening Committee	Update to reflect current process for Screening Committee review.
	Previous version : Inclusion and exclusion criteria assessed.	
Section 5.5 Pre- Screening/Screening	Addition of : "Angiography and/or CTA" as a requirement for the Pre- Screening/Screening visit	Update to reflect current process for Screening Committee review.
Section 5.5 Pre- Screening/Screening	Addition of: Pre-screening Assessment A Screening Committee will review pre-operative angiography and/or CTA, along with patient medical history, for assessment of entry criteria, and approval prior to the study procedure. The Screening Committee will be comprised of an interdisciplinary team of study investigators with pertinent	Update to reflect current process for Screening Committee review.

CONFIDENTIAL INFORMATION MD133246 Protocol Template Revision#: 1 Doc Type: GC

knowledge in carotid stenting. The members will not review potential cases from their own sites. The members will be compensated for their involvement in the Screening Committee, including reimbursement for reasonable travel expenses to attend meetings.	
This committee will operate under pre-specified procedures as outlined in the Screening Committee Charter.	
Prior to a patient being enrolled in the study, the investigational site must receive confirmation from the Screening Committee that the subject is eligible to be enrolled. Although patient may be deemed eligible to be enrolled, it is still the responsibility of the investigator to assess all inclusion and exclusion criteria prior to enrollment.	
Screening Angiogram and/or CTA	
In addition to review of medical history, patients will be screened by the Screening Committee based on the results of an angiogram or CTA. These images must include at a minimum the aortic arch, ipsilateral carotid artery, target lesion, and intracranial and extracranial views. A complete diagnostic study will be needed in order to evaluate fully the patient against entry criteria. Submission of complete case images is	
	potential cases from their own sites. The members will be compensated for their involvement in the Screening Committee, including reimbursement for reasonable travel expenses to attend meetings. This committee will operate under pre-specified procedures as outlined in the Screening Committee Charter. Prior to a patient being enrolled in the study, the investigational site must receive confirmation from the Screening Committee that the subject is eligible to be enrolled. Although patient may be deemed eligible to be enrolled, it is still the responsibility of the investigator to assess all inclusion and exclusion criteria prior to enrollment. Screening Angiogram and/or CTA In addition to review of medical history, patients will be screened by the Screening Committee based on the results of an angiogram or CTA. These images must include at a minimum the aortic arch, ipsilateral carotid artery, target lesion, and intracranial and extracranial views. A complete diagnostic study will be needed in order to evaluate fully the patient against entry criteria. Submission of

Section 5.6 Pre-Procedure Assessments	Current version : Baseline Cardiac Enzyme -Troponin (may be obtained once arterial access is gained but not after any interventional wires enter the subject's vasculature	Added additional clarification as to when cardiac Troponin may be drawn.
	Previous version: Baseline Cardiac Enzyme (Troponin)	
Section 5.6 Pre-Procedure Assessments	Current version : Concomitant Medications (antiplatelet and anticoagulant therapy)	Clarify which medications are being collected
	Previous version:	
	 Concomitant medications 	
	Assess Antiplatelet Therapy	
Section 5.7 Procedure	Current version : Concomitant Medications (antiplatelet and anticoagulant therapy)	Clarify which medications are being collected
	Previous version : Concomitant medications	
Section 5.10 Post-Procedure	Current version : Concomitant Medications (antiplatelet and anticoagulant therapy) assessment	Clarify which medications are being collected
	Previous version:	
	Concomitant medications	
Section 5.11 Follow-Up	Current version : Concomitant Medications (antiplatelet and anticoagulant therapy) assessment	Clarify which medications are being collected
	Previous version:	
	Concomitant medications assessment	
Section 6.4 Core Labs	Current Version:	Update to reflect change in address for address .

GORE® Carotid Stent MD134865 GCS 10-08 PROT Revision#: 3 Doc Type: SP

	Previous Version:	
Section 6.5 Protocol Deviations	Current Version: A Protocol Deviation is defined as any change, divergence, or departure from the study design or procedures of a research protocol. The Investigator is responsible for promptly reporting Protocol Deviations to their reviewing IRB per IRB policy and the Sponsor. Previous Version : A protocol deviation is defined as any change, divergence, or departure from the study design or procedures of a research protocol that is under the Investigator's control and that has not been approved by the IRB/EC. The Investigator is responsible for promptly reporting protocol deviations to their IRB/EC per IRB/EC policy and the Sponsor.	Update to reflect the current protocol template wording
Sections 6.5, 6.6, 6.8, and 6.9 Section 6.9	Removed all 'EC' from IRB/EC regulatory referencesCurrent version:Records will be maintained during the clinical study and for a minimum of two years after the latter of the date on which the study is terminated or completed, or the date the	Update to reflect study will be in the U.S. only. Update to reflect the current protocol template wording.
	records are no longer required to support regulatory approval of the device.	

CONFIDENTIAL INFORMATION MD133246 Protocol Template

	Previous version: Records will be maintained during the clinical study and three years after the day on which marketing authorization of the investigational device is obtained or three years after the date of discontinuation or completion of the clinical trial, whichever comes later.	
Section 9.1.1 Adverse Event Relationship	Addition of:Only one primary relationship will be assigned to each reported AE.Study Device-relatedCurrent version:The functioning or characteristics of the device caused or contributed to the Adverse Event.Previous version:If the functioning or characteristics of the stent caused or contributed significantly to the adverse event, the adverse event would be suspected as primarily related to the stent.	Update to reflect the current protocol template wording. Update to reflect the current protocol template wording.
	Embolic Protection System (EPD)-related Current version : The functioning or characteristics of the EPD caused or contributed to the Adverse Event. Previous version : If the functioning or characteristics of the EPD caused or contributed significantly to the adverse event, the adverse event would be suspected as primarily related to the EPD.	Update to reflect the current protocol template wording.

Study Procedure-related Current version: The study index procedure (and not the device or EPD) caused or significantly contributed to the Adverse Event.	Update to reflect the current protocol template wording.
Previous version : If the procedure (and not the device) caused or significantly contributed to the adverse event, the adverse event would be suspected as primarily related to the procedure.	
Medication-related Current version : The Adverse Event was a result of medical therapy prescribed by the study protocol and not the device, EPD, or procedure.	Update to reflect the current protocol template wording.
Previous version : If the adverse event was a result of a medication taken as part of the study/procedure, the adverse event would be suspected as primarily related to the medication.	
Disease-related Current version : The Adverse Event was a result of the underlying disease progression for which the study procedure is being performed, and not the device, EPD or procedure.	Update to reflect the current protocol template wording.
Previous version : If the adverse event was a	

	result of the underlying disease progression for which the study procedure is being performed, and not the device or procedure, the adverse event would be suspected as primarily related to the disease. Not related Current version : An Adverse Event which	Update to reflect the current protocol template wording.
	cannot be attributed to the device, EPD, procedure, medication or disease.	
	Previous version: If an adverse event cannot be attributed to the device, procedure, medication, or disease, it will be reported as "Not related".	
	Unknown relationship Current version : The relationship of the Adverse Event to the device, EPD, procedure, medication or disease cannot be determined.	Update to reflect the current protocol template wording.
	Previous version: If the relationship of the adverse event to the device, procedure, medication, or disease cannot be determined, it will be coded as "Unknown".	
Section 9.2 Unanticipated Adverse Device Effect	Removed 'EC' from IRB/EC regulatory references	Update to reflect study will be in the U.S. only.
(UADE)	Addition of: A report from the Sponsor will be submitted to the FDA and to all reviewing IRBs and participating Investigators within 10 working days after the Sponsor first receives notice of the effect.	Update to reflect the current protocol template wording.

Section 10.4.3 Analysis Sets	Current Version : The primary analysis set for testing of the primary endpoint is the per- protocol analysis set. Previous Version : The primary analysis set for testing of the primary endpoint is the intent- to-treat, or full, analysis set.	Because subjects with technical failure are followed only to 30 days, they will not be evaluable for the primary endpoint. The ITT set includes technical failures; the per-protocol set does not.
Section 10.4.3 Intent-To- Treat Analysis Set	Current Version : The ITT analysis set is defined as all enrolled subjects with adequate informed consent, regardless of whether the study stent was implanted. Because technical failures (test device attempted but not implanted) are followed only to 30 days, this set will be used in the analysis of safety endpoints (major, serious, and nonserious adverse events) to 30 days and secondary endpoints evaluated at procedure, discharge, and 30 days. Previous Version : The ITT analysis set is defined as all enrolled subjects with adequate informed consent, regardless of whether or not the study stent was implanted. This set will be used in the analysis of the primary and all secondary endpoints evaluated at procedure, 30 days and one year, as well as supplemental analyses of the primary endpoint (for example, Kaplan- Meier survival analysis).	Same as above.
Section 10.4.3 Per-Protocol Analysis Set (Primary Analysis Set)	Current Version : For per- protocol analysis, only subjects who had the study stent implanted in the target vessel and had no major protocol deviations will be included in the analysis. Major protocol deviations are defined as protocol deviations with a level	Same as above, plus clarification to definition of major protocol deviation.

of seriousness such that inclusion of the subject(s) would unacceptably bias the primary endpoint analysis. An example of a major protocol	
deviation might be failure to satisfy eligibility criteria to a degree where the subject does not fit the underlying scientific model for the treatment.	
The per-protocol set will be used for the primary analyses of the primary endpoint. Ideally, this analysis set will consist of all subjects from the ITT set with technical success (test device implanted).	
Per-Protocol Analysis Set (Primary Analysis Set)	
Previous Version : For per- protocol analysis, only subjects who had the study stent implanted in the target vessel and had no major protocol deviations will be included in the analysis. Anticipated major protocol deviations are defined as any of the following:	
Subject does not satisfy inclusion/exclusion criteria	
 Inadequate informed consent 	
Per-Protocol Analysis Set	

MD134865 GCS 10-08 PROT Revision#: 3 Doc Type: SP

11.1 Statement of Compliance	Removed referen global data can k submission in the Japan"	be used for	Update to reflect study will be in the U.S. only.
	Removed the following local regulatory requirements:2005 Ministry of Health, Labor and OrdinanceMinisterial OrdinanceLabor and Welfare Ordinanceon Good Clinical Practice for Medical DevicesMedical DeviceDevicesMedical 		Update to reflect study will be in the U.S. only.
		and of the Council of 5 September 2007	
	Removed the fol sentence: The S obtain clinical tria as required by th country in which conducted.	ponsor will als insurance e laws of each	Update to reflect study will be in the U.S. only.
Section 11.2 Compliance Responsibilities	Removed all 'EC regulatory refere		Update to reflect study will be in the U.S. only.
	Removed Careta location in Japan		Update to reflect study will be in the U.S. only.
Sections 11.3, 11.4 and 11.6	Removed all 'EC regulatory refere		Update to reflect study will be in the U.S. only.

PROTOCOL SUMMARY

PROTOCOL SUMMARY					
Study Title	GORE® Carotid Stent Clinical Study for the treatment of carotid artery stenosis in patients at increased risk for adverse events from carotid endarterectomy				
Protocol Number	GCS 10-08				
Amendment 3	22 OCT 2014				
Amendment 2	10 JUL 2013				
Amendment 1	04 FEB 2013				
IDE Number	G110127				
Sponsor	W. L. Gore & Associates, Inc. Medical Products Division [name] [contact]				
Study Design	Multicenter, single-arm, prospective study comparing the GORE® Carotid Stent to a performance goal developed from carotid endarterectomy (CEA) outcomes				
Study Objective	To evaluate the safety and effectiveness of the GORE® Carotid Stent for the treatment of carotid artery stenosis in patients at increased risk for adverse events from carotid endarterectomy.				
Study Endpoints	 Primary Endpoint: Major Adverse Event (MAE) rate defined as a composite of: Death, stroke, or MI through 30 days post-index procedure, and Ipsilateral stroke from Day 31 through 1 year Secondary Endpoints: Stent Technical Success Embolic Protection Technical Success Procedure Success In-Stent Restenosis Target Lesion Revascularization 				
Subject Population	Patients at least 18 years of age who have either de novo atherosclerotic or postendarterectomy restenotic lesions in the internal carotid arteries or at the carotid bifurcation, with either ≥50% (by angiography) stenosis if symptomatic (stroke, TIA, TMB within 180 days of procedure), or ≥80% (by angiography) stenosis if asymptomatic. Patients must have either anatomic or medical co-morbidities that place them at high perioperative risk for CEA.				
Number of Subjects	312				
Number of Clinical Investigative Sites	Up to 50 sites in the U.S.				
Study Duration	Time to Complete Enrollment: 18-24 months Follow-up Time: 36 months Total Study Duration: 54-60 months				

CONFIDENTIAL INFORMATION MD133246 Protocol Template

Follow-up Schedule	Screening, Pre-procedure, Procedure, Post-Procedure, 30				
Follow-up Schedule	days, 6 months, 1 year, 2 years, and 3 years				

LIST OF ABBREVIATIONS

	LIST OF ABBREVIATIONS
ACT	Activated Clotting Time
AE	Adverse Event
BUN	Blood Urea Nitrogen
CAS	Carotid Artery Stenting
CBC	Complete Blood Count
CCA	Common Carotid Artery
CDUS	Carotid Duplex Ultrasound
CDMS	Clinical Data Management System
CEA	Carotid Endarterectomy
CEC	Clinical Events Committee
CFR	Code of Federal Regulations
CHF	Congestive Heart Failure
Cm	Centimeters
COPD	Chronic Obstructive Pulmonary Disease
CRF	Case Report Form
СТ	Computed Tomography
СТА	Computed Tomographic Angiography
DSMB	Data and Safety Monitoring Board
EC	Ethics Committee
ECA	External Carotid Artery
eCRF	Electronic Case Report Form
ECG	Electrocardiogram
ePTFE	Expanded Polytetrafluoroethylene
FDA	Food and Drug Administration (United States)
Fr	French (sizing)
GCP	Good Clinical Practice
HIT	Heparin-Induced Thrombocytopenia
ICA	Internal Carotid Artery
ICF	Informed Consent Form
ICH	International Conference on Harmonization
IDE	Investigational Device Exemption
IFU	Instructions for Use
INR	International Normalized Ratio
IRB	Institutional Review Board (U.S.)
LVEF	Left Ventricular Ejection Fraction
MI	Myocardial Infarction
mm	Millimeters
MRA	Magnetic Resonance Angiography
MRI	Magnetic Resonance Imaging
NASCET	North American Symptomatic Carotid Endarterectomy Trial

GORE® Carotid Stent MD134865 GCS 10-08 PROT Revision#: 3 Doc Type: SP

- NIHSS National Institute of Health Stroke Scale
- NYHA New York Heart Association
- PFO Patent Foramen Ovale
- PG Performance Goal
- PMA Premarket Approval
- SAE Serious Adverse Event
- TIA Transient Ischemic Attack
- TLR Target Lesion Revascularization
- UADE Unanticipated Adverse Device Effect

1.	INTRODUCTION	20

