5.3. Informed Consent Process

All patients must provide written informed consent prior to submission of pre-procedure imaging and medical history to the Screening Committee for review (refer to Section 5.5 for details) and prior to any study related procedures being performed. The case history (i.e. source documents/subject chart) for each subject shall document that such informed consent was obtained. The IRB approved consent form will be signed and personally dated by the subject, and the person who conducted the informed consent discussion. The original signed informed consent form will be retained in the subject records. A copy of the informed consent document will be given to the subject for their records.

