5.5. Pre-Screening/Screening

All patients who sign an ICF will be considered entered into the screening phase of the study.

A subject screening log will be maintained at each site to document select information about the patients who sign informed consent. For patients who did not meet eligibility criteria **after** signing informed consent, the reasons for exclusion will be documented on the subject screening log.

The following evaluations will be conducted at the **screening visit** or must have been completed no more than 30 days prior to enrollment (except as noted):

• Informed consent (prior to any study related procedures being performed)

GORE CONFIDENTIAL INFORMATION

- Inclusion and exclusion criteria assessed; confirmation is required by Screening Committee
- Assess medical history, demographics, and concomitant medications
- Modified Rankin Scale
- 12-lead ECG
- Examination and vital signs
- Chemistry (BUN & Creatinine)
- Hematology (CBC including platelets)
- Bilateral Carotid Duplex Ultrasound (within the 60 days preceding the index procedure)
- Angiography (within 30 days) and/or CTA (within 60 days)
- CT or MRI Brain Imaging for symptomatic patients only (Within 180 days of the index procedure)I

Pre-screening Assessment

A Screening Committee will review pre-operative angiography and/or CTA, along with patient medical history, for assessment of entry criteria, and approval prior to the study procedure.

The Screening Committee will be comprised of an interdisciplinary team of study investigators with pertinent knowledge in carotid stenting. The members will not review potential cases from their own sites. The members will be compensated for their involvement in the Screening Committee, including reimbursement for reasonable travel expenses to attend meetings.

This committee will operate under pre-specified procedures as outlined in the Screening Committee Charter.

Prior to a patient being enrolled in the study, the investigational site must receive confirmation from the Screening Committee that the subject is eligible to be enrolled. Although patient may be deemed eligible to be enrolled, it is still the responsibility of the investigator to assess all inclusion and exclusion criteria prior to enrollment.

Screening Angiogram and/or CTA

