In addition to review of medical history, patients will be screened by the Screening Committee based on the results of an angiogram or CTA. These images must include at a minimum the aortic arch, ipsilateral carotid artery (origin and bifurcation), target lesion and intracranial and extracranial views. A complete diagnostic study will be needed in order to evaluate fully the patient against entry criteria. Submission of complete case images is strongly encouraged.

Carotid Duplex Ultrasound

Patients will be screened using a bilateral carotid duplex ultrasound within 60 days of enrollment to verify that baseline percent stenosis values are consistent with entry criteria and justify proceeding with angiography and stent placement.

The diagnostic angiography results prior to the stenting procedure will be the definitive measure of compliance with vessel stenosis criteria.

If a bilateral carotid duplex ultrasound was completed prior to the patient's consent to participate in the clinical trial but is within 60 days preceding the study procedure, the results may be used in lieu of repeating the ultrasound for the clinical trial.

MRI / CT for Symptomatic Patients

CT or MRI brain imaging is required for symptomatic patients in order to rule out non-carotid pathology. Additional assessment of the carotid arteries and the morphology of the aortic arch may be achieved through CTA or MRA but the results of these studies may not be used as a substitute for a carotid ultrasound or carotid angiography. If CT or MRI brain imaging was completed at the time of the "symptomatic" event (within 180 days) and is prior to the patient's informed consent to participate in the clinical trial, the CT or MRI results obtained following that event may be used in lieu of repeating the imaging for the clinical trial.

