5.8. Enrollment

The patient will be considered enrolled in the study when the investigational device enters the patient's vasculature. All patients enrolled in the study should be followed until completion of the study, or withdrawal from study follow-up.

If the decision is made not to attempt the GORE® Carotid Stent and therefore not enroll the patient, the patient will be considered a screen failure and the status and reason for not enrolling noted on the subject screening log.

A patient may only be enrolled into the study once. A patient with carotid artery disease contralateral to the target lesion in which both sides require treatment may be enrolled into the study; however, only one side may be treated at the index procedure.

Embolic Protection System

The investigator must select the GORE® Embolic Filter for embolic protection during the procedure and should pay specific attention to the device IFU for specific patient selection criteria.

After an unsuccessful documented attempt with the GORE® Embolic Filter, an alternative locally approved embolic protection device may be used to complete the procedure.

Unprotected pre-dilation is strongly discouraged. Embolic protection with the GORE® Embolic Filter should be in place prior to stenting.

GORE® Carotid Stent

Selection of the correct size GORE® Carotid Stent should be done using the sizing instructions in the table below and/or the IFU for the device. Oversizing of the stent to the vessel diameter is not recommended.

	GORE® Carotid Stent Part Number	Unconstrained Stent Dimensions	Reference Vessel Diameter	Minimum Introducer or Guiding Sheath Catheter I.D.		
	GCS5530	5 x 30 mm	3.7-4.5 mm	-		
	GCS5540	5 x 40 mm	5. 1- 4.5 mm			
	GCS6630	6 x 30 mm	4.5-5.4 mm			
	GCS6640	6 x 40 mm	4.5-5.4 11111			
5F	GCS7730	7 x 30 mm	5.4-6.3 mm	074" (1.99 mm)		
55	GCS7740	7 x 40 mm	5.4-0.3 1111	074" (1.88 mm)		
	GCS8830	8 x 30 mm	6.3-7.2 mm			
	GCS8840	8 x 40 mm	0.3-7.2 11111			
	GCS6830	6-8 x 30 mm taper	4.5-5.4 mm x 6.3-7.2 mm			
	GCS6840	6-8 x 40 mm taper	4.5-5.4 1111 x 0.5-7.2 1111			
	GCS9930	9 x 30 mm	7.2-8.1 mm			
	GCS9940	9 x 40 mm	7.2-0.11111			
	GCS0030	10 x 30 mm	8.1-9.0 mm			
6F	GCS0040	10 x 40 mm	0.1-9:011111	080" (2.03 mm)		
	GCS7930	7-9 x 30 mm taper	5.4-6.3 mm x 7.2-8.1 mm			
	GCS7940	7-9 x 40 mm taper	5.4-0.5 mm x 7.2-0.1 mm			
	GCS8030	8-10 x 30 mm taper	6.3-7.2 mm x 8.1-9.0 mm			
	GCS8040	8-10 x 40 mm taper	0.3-7.2 1111 X 8. 1-9.0 11111			

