9.1.3. Adverse Event Reporting and Coding

AEs will be reported on the appropriate case report form (CRF) for that visit and documented in the subject's permanent medical record. The Investigator at each Site is ultimately responsible for reporting AEs to the Sponsor.

The following information on each reported Adverse Event will be collected:

- Adverse Event Name
- Adverse Event Onset Date
- Relationship
- Classification Serious
- Treatment
- Outcome
- Resolution Date

Adverse Events will be coded using the Medical Dictionary for Regulatory Activities (MedDRA).

Adverse event submission guidelines:

- Adverse event reporting begins once the patient is enrolled in the study. All adverse events should be reported from enrollment through study completion/discontinuation.
- Provide a diagnosis if possible. If unable to provide diagnosis, report the symptoms as separate events. Adverse Events should be reported using the full name without abbreviations or narratives.
- Adverse events with an outcome status of "Ongoing" should be assessed at each follow-up evaluation to determine if the event has resolved. Adverse events ongoing at study completion/discontinuation should be left as "Ongoing" on the AE case report form.

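### Complications of screening angiography or CTA performed for the study are not captured as adverse events, because collection starts only at stent entry

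*Protocol*

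**What the plan says.** **Imaging before enrollment.** Protocol Section 5.5 lists among the screening evaluations "Angiography (within 30 days) and/or CTA (within 60 days" (the bracket closes there). On committee review it says "A Screening Committee will review pre-operative angiography and/or CTA, along with patient medical history, for assessment of entry criteria". On the content of the images it adds that "A complete diagnostic study will be needed in order to evaluate fully the patient against entry criteria". Before any patient is enrolled, "the investigational site must receive confirmation from the Screening Committee that the subject is eligible to be enrolled".

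**Consent.** Section 5.3 states that "All patients must provide written informed consent prior to submission of pre-procedure imaging and medical history to the Screening Committee for review", and also before any study-related procedure. Under Section 5.5 a patient who signs is in the screening phase.

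**Existing imaging.** Screening evaluations are done at the screening visit or "must have been completed no more than 30 days prior to enrollment (except as noted"; the exceptions include the longer CTA window.

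**Start of safety collection.** Protocol Section 9.1.3: "Adverse event reporting begins once the patient is enrolled in the study". Section 5.8: "The patient will be considered enrolled in the study when the investigational device enters the patient's vasculature". SAP Section 2.3 uses the same definition. In the schedule of events (Section 5.2) the adverse event row is first marked in the Procedure/Enrollment column. SAP Section 4.5 groups onset as procedure, pre-discharge and post-discharge.

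**Patients who do not go on.** Sections 5.5 and 5.8 send the reason for exclusion, or for not attempting the stent, to the site screening log.

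**The concern.** The screening imaging covers the arch, the carotid and the intracranial and extracranial vessels. If suitable recent films do not exist, a consented patient has contrast imaging because the study requires it, and that may be a catheter study. It is a separate procedure from the index procedure and may precede it by up to 30 days (angiogram) or 60 days (CTA). The protocol attaches no adverse event collection to it.

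Subject protection and complete safety reporting are at stake. The DSMB is asked to advise on the continuing safety of study subjects, and the plan gives it no stated means of seeing harm from a step that the protocol itself requires. Moving the start of reporting to vascular access at the index procedure would not close the gap, since the imaging comes earlier.

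**Working it through.** The documents give no figure to reproduce. The main check is to set the rules side by side; the size needs assumptions.

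**1. Order of events**

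1. Consent (Protocol 5.3)
2. Screening angiogram or CTA, if not already available (5.5)
3. Screening Committee confirmation (5.5)
4. Vascular access, where the index procedure begins (5.7)
5. Stent enters the vasculature: enrollment (5.8; SAP 2.3), and adverse event reporting begins (9.1.3)

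Screening imaging always falls before step 5, so by Section 9.1.3 its complications are outside reporting. Section 5.7 lists adverse event assessment under the procedure, which leaves the interval between steps 4 and 5 ambiguous. That should be reconciled too, but it does not reach back to step 2.

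**2. Whether another part of the plan would catch these events**

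- *Schedule (5.2):* no adverse event mark at Screening or Pre-procedure.
- *Relationship categories (9.1.1):* the procedure category refers to the index procedure.
- *SAP 4.5:* no onset category before the procedure. Denominators are drawn from enrolled subjects in the analysis set, so screen failures do not appear.
- *Clinical Events Committee (9.4; SAP 3.4):* acts on potential primary endpoint events reported by sites. That endpoint (3.2.2) is timed from the index procedure.
- *NIHSS (5.6):* done within 24 hours before the procedure. A deficit caused by earlier imaging would be part of the baseline.
- *BUN and creatinine (5.2):* scheduled once, at screening or pre-procedure. If drawn before the imaging, contrast-related renal injury is not measured unless an unscheduled test is clinically indicated.
- *Eligibility (4.2, 4.3):* evolving, acute or recent disabling stroke excludes, but a non-disabling stroke in the target hemisphere within 180 days meets the symptomatic definition. A patient with a non-disabling stroke from the imaging, once no longer acute, could be enrolled with no screening-log reason at all.

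None of these records the complication as an adverse event.

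**3. Size, under assumptions**

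The documents state neither how many patients N have catheter angiography solely for the study nor its neurological risk r (stroke or TIA). Assume N = 100 to 312, where 312 is the full planned enrollment and so illustrative rather than a central estimate, and r = 0.3% to 1.0%.

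Expected events = N × r. Chance of at least one = 1 − (1 − r)^N.

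| N | r | Expected events | Chance of at least one |
|---|---|---|---|
| 100 | 0.003 | 100 × 0.003 = 0.3 | 1 − 0.997^100 = 26% |
| 100 | 0.010 | 100 × 0.010 = 1.0 | 1 − 0.990^100 = 63% |
| 312 | 0.003 | 312 × 0.003 = 0.94 | 1 − 0.997^312 = 61% |
| 312 | 0.010 | 312 × 0.010 = 3.12 | 1 − 0.990^312 = 96% |

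Access-site, contrast and renal complications would be additional. As N falls towards zero, so do both quantities.

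**The case against.** The strongest reply is that starting collection at device entry is a deliberate choice, stated consistently in both documents, and that the extra exposure may be small. Much of this stands:

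- Committee review can rest on CTA alone, so catheter angiography is not required at screening.
- Films obtained before consent are accepted, and candidates should already have a diagnosis of carotid stenosis (4.1).
- An angiogram from the preceding 30 days may replace the diagnostic angiogram at the index session (5.7). A catheter study at screening can therefore bring an exposure forward rather than add one.

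These points limit how many patients are affected. They do not supply a reporting route for those who are.

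Three stronger readings are tempting, and the documents do not support them:

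- *Such harm is never recorded or reviewed.* A complication that makes the patient ineligible can leave a reason on the screening log, and the pre-procedure examination and NIHSS may show a new deficit. The DSMB and Clinical Events Committee charters are not among the documents, so absence of any review cannot be shown.
- *The trial's safety result is too favourable.* The primary endpoint is counted from the index procedure and tested in implanted per-protocol subjects, so it is unaffected by design. The documents make no safety claim for the whole pathway including screening. The performance goal derivation is not shown, so whether its source data counted pre-operative imaging harm is unknown.
- *At least one unrecorded neurological event is likely.* The 61% to 96% range treats all 312 planned subjects as having catheter angiography because of the study. The documents do not support that number.

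**Conclusion.** The concern holds as a gap in safety collection. Between consent and stent entry the plan sets out no adverse event collection for screening imaging. Complications of an angiogram or CTA performed for the study are not captured as adverse events and have no defined route to safety review; a screening-log reason is the most that is kept, and only if the patient does not go on.

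The number of patients affected cannot be determined from the documents and may be near zero. Under the stated assumptions (100 to 312 patients with study-driven catheter angiography, 0.3% to 1.0% neurological risk), 0.3 to 3.1 events are expected and the chance of at least one is 26% to 96%. Neither range comes from the documents. The primary endpoint result does not change. The case for acting is that the protocol requires the step and that collecting its harms costs little.

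**What to change.** - **Protocol 9.1.3:** for consented patients whose screening angiogram or CTA was performed for this study, record deaths, strokes and TIAs, other serious adverse events, and access-site, contrast or renal complications that the site becomes aware of. The window runs from the imaging until enrollment or, for screen failures, until the date screen failure is logged.
- **Protocol 5.2:** mark an adverse event assessment after screening imaging and before the index procedure. A mark at the screening visit alone could fall before the imaging is done.
- **SAP 4.5:** list these events separately, with patients imaged for the study as the denominator, outside the primary endpoint numerator.
- **DSMB reports:** include the listing.

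The cost is wording in two documents and one short form, which sites would also complete for some screen failures. No visits or procedures are added, because collection is limited to what the site learns in the ordinary course. The price of that limit is that complications appearing after screen failure is logged may still be missed.
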